6. CONSENT

Written informed consent will be obtained at the beginning of the study visit. By this point the participant will have already received and had a chance to read the participant information sheet and ask any questions during their recruitment telephone conversation with the PI.

7. ELIGIBILITY CRITERIA

7.1. Inclusion Criteria

- Able to understand written English without the need for an interpreter,
- No diagnosed communication impairment
- Endoscopically confirmed primary ENT diagnosis of either:
 1. muscle tension dysphonia (with no laryngeal abnormality),
 2. Vocal fold palsy
 3. Presbylaryngis.

7.2. Exclusion Criteria

- Under 18 years of age or over 90 years of age.
- Previous SLT input
- Any of the following possible contraindications for PEP therapy:
 - Inability to tolerate increased work of breathing,
 - ICP (intracranial pressure) > 20mm Hg,
 - Recent facial/oral/skull surgery or trauma,
 - Oesophageal surgery,
 - Untreated pneumothorax,
 - Known or suspected tympanic membrane rupture/other middle ear pathology,
 - Haemodynamic instability,
 - Acute sinusitis,
 - Epistaxis,
 - Active haemoptysis,
 - Nausea

8. RECRUITMENT

Whenever possible, participants are to be preferentially recruited from within joint- or Speech Therapy-led voice clinics (four in total each week). In this way, a member of the Speech Therapy team who has knowledge of the study and the inclusion criteria can assist in making a preliminary assessment of the participant's suitability for the study. The participant will then be given a brief verbal explanation of the study and a participant information sheet to take away with them.

As a result of significantly reduced patient numbers in joint voice clinics, and the temporary halting of Speech Therapy-led voice clinics (both as a result of Covid-19 precautions), participants may *alternatively* be identified from the waiting list of patients referred to ENT Speech Therapy by an ENT consultant but who have not yet received voice therapy. In this way, the PI will be able to review the patient's video recorded laryngeal exam and make an assessment of their suitability for the study. Those who are suitable will be contacted via telephone and given a brief verbal explanation of the study and a participant information sheet put in the post for those who are interested in finding out more.

The prospective participant will then be telephoned by the PI during the following week. The PI will ask over the telephone whether they have any of the contraindications for PEP which would result in their being deemed unsuitable for inclusion in the study and will answer any

questions the participant might have. Should they meet all inclusion criteria, the PI will then set up a day and time to come in, give informed consent, and participate in a single research session lasting around one hour. Should they not be eligible for inclusion in the study, this will be documented in the study file's Screening Log.

This research session will complete the subject's involvement in the study, and they will then be returned to the normal clinical pathway and receive Speech Therapy input as indicated and in a timely fashion dependent on their place on the waiting list. Participants will be compensated for their time with a £10 gift voucher and their travel expenses will be reimbursed up to a maximum of £12.50 (London Zone 1-6 daily cap) providing presentation of valid receipts.

9. STATISTICAL METHODS

As this is a feasibility study and this is the first time that this particular exercise has been trialled in pathological voice, effect sizes are as yet unknown. The decision to recruit 10 participants of each voice type was informed by a recent audit of departmental referrals (January 2015 to July 2017). Over this period, we received an average of 57 referrals per month. Monthly referrals for MTD account for 15.8% of that total (9), referrals for vocal fold palsy account for 6.5% (4) and referrals for presbylaryngis account for 5.9% (3). It was felt that 10 of each group was reasonable to recruit within the planned timescale of the study (initially, 12 months, but owing to a significant drop in throughput of patients in voice clinics as a result of Covid-19, this timescale has been extended to 18 months), large enough to inform about the practicalities of recruiting for a larger future study and large enough to provide some indication of the effects of each treatment on baseline variables.

Despite it being unclear what effects will be seen in these clinical populations, our previous pilot using normophonic volunteers was able to identify statistically significant change in sound pressure level (SPL) and mean flow during voicing, both biologically relevant changes for voice production. For this study, descriptive statistics will be used and will include box plots, means/medians, standard error and tests of significant differences between groups and exercises will be carried out using ANOVAs. Baseline data for consideration will include expert-rated perceptual, acoustic, aerodynamic and electroglottographic measures of the voice.

Questionnaire data will also be collected and will be analysed for pre-post changes in self-rated voice quality and ease of voice production. Views on the exercises (i.e. ease of use, portability, likelihood of carrying out task if it were given in a therapy programme) will also be compared between exercises and between groups.

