3.2. Secondary Objectives

To identify whether this patient group is able to make use of Acapella Choice for this purpose

To identify if this intervention can be incorporated into the standard patient clinical pathway

To identify if sufficient subjects can be recruited and retained

To identify sample sizes for possible future research

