4. STUDY DESIGN

This is a feasibility study using a ‘before and after’ design to test the immediate effects of exercising with Acapella Choice in comparison to the immediate effects of exercising with Tube. Dysphonic subjects will be recruited from referrals received from four RNTNE-based voice clinics with an endoscopically-confirmed diagnosis of muscle tension dysphonia (MTD), presbylaryngis (age-related vocal fold atrophy) or vocal fold palsy. They will attend only one research session which will last approximately one hour.

The aim is to recruit ten subjects from each diagnosis for a total of 30 patients. As this is a feasibility study, a sample size calculation has not been performed. Instead, the target number for recruitment is instead informed by a recent audit of referrals to the department.

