5. STUDY SCHEDULE

Enrolment will begin from day one of the study. Prospective participants will be identified by the Speech Therapist in attendance at voice clinics held at the Royal National Throat Nose and Ear Hospital. The therapist will briefly explain the study, give the patient and information sheet, and get consent for the PI to contact them over the following week to carry out a telephone screening of their eligibility.

Following successful screening by the PI, the participant will be given an appointment to attend an approximately one hour long research session where the interventions will be carried out and data collected. This single session will conclude the participant’s involvement in the study, and they will return to their ordinary clinical pathway, awaiting commencement of their Speech Therapy input, as indicated. There will be no study follow-up for participants.

A participant may withdraw at any time and their normal clinical pathway from referral to treatment will remain unaffected.

The end of the study will be reached as soon as the target number of participants has been recruited, or eighteen months has elapsed from the commencement of the study, whichever comes first.

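### Does the objective of identifying future sample sizes need its own method in Section 9?

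*Combined protocol and SAP*

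**What the plan says.** Among the secondary objectives in Section 3.2 of the protocol is "To identify sample sizes for possible future research". Section 4 describes a before-and-after design meant "to test the immediate effects of exercising with Acapella Choice in comparison to the immediate effects of exercising with Tube", and Section 1 has each patient do both exercises in a single session, so the data are paired. For the present study, Section 4 states that "As this is a feasibility study, a sample size calculation has not been performed", and "The aim is to recruit ten subjects from each diagnosis for a total of 30 patients".

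Section 9 says that effect sizes are not yet known and bases the target of 10 per diagnosis on a referral audit. For the analysis, "descriptive statistics will be used and will include box plots, means/medians, standard error", with ANOVAs to test differences between groups and between exercises. On the measures, "Baseline data for consideration will include expert-rated perceptual, acoustic, aerodynamic and electroglottographic measures of the voice". Questionnaire answers are to be analysed for change from before to after exercise and compared between exercises and groups. Section 9 does not say how a future sample size would be obtained.

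**The concern.** A listed objective would normally have a matching line in the analysis section, and this one has none. Four families of voice measure and a questionnaire are collected, and none is marked as the basis for sizing. The two outcomes mentioned by name, sound pressure level and mean flow, appear only as findings of the earlier pilot in people with normal voices.

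The standard error is also ambiguous. If it is the standard error of a raw score, multiplying by the square root of n returns the raw SD. That does not give the SD of a within-person change unless the correlation between the two measurements is known. If only raw-score summaries were published, an outside team planning another within-person study would have to guess that correlation. No confidence interval is mentioned either, although an SD from 10 people is imprecise.

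**Working it through.** **The plan's own figures.** There is no power or precision calculation to reproduce. The counts agree with each other: 3 × 10 = 30, and from 57 referrals a month, 57 × 0.158 = 9.0, 57 × 0.065 = 3.7 and 57 × 0.059 = 3.4, which round to the stated 9, 4 and 3.

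**How much the choice of SD matters.** With equal variances before and after, Var(change) = 2(1 − ρ) × Var(raw), where ρ is the within-person correlation. The documents give no ρ, so a range is assumed. The sample sizes below are for a paired t-test with an assumed target change of 0.5 raw SD, 80% power and two-sided 5%. The standardised effect is 0.5 / √(2(1 − ρ)).

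| Assumed ρ | Var(change) / Var(raw) | Standardised effect | Patients |
|---|---|---|---|
| 0.5 | 1.0 | 0.50 | 34 |
| 0.7 | 0.6 | 0.65 | 21 |
| 0.8 | 0.4 | 0.79 | 15 |
| 0.9 | 0.2 | 1.12 | 9 |

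The variance ratio across this range is 1.0 / 0.2 = 5. The t-test sample sizes differ by 34 / 9 = 3.8, less than five-fold because small samples pay a penalty for estimating the SD.

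For the Acapella–Tube difference in change, with a separate baseline for each exercise and equal correlations, the variance is 4(1− ρ) times the raw variance. The corresponding sizes are 65, 40, 28 and 15, a ratio of 65 / 15 = 4.3.

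**How precise an SD from this study would be.** The 95% limits for an SD, as multiples of the estimate, are √(df / χ²₀.₉₇₅) and √(df / χ²₀.₀₂₅).

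- One diagnosis, n = 10, 9 df: √(9 / 19.02) = 0.69 and √(9 / 2.70) = 1.83. Sample size scales with the variance, so by a normal approximation a future size would carry a factor of 0.47 to 3.33.
- Three diagnoses pooled, 27 df, common variance assumed: √(27 / 43.19) = 0.79 and √(27 / 14.57) = 1.36.

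These multipliers need only the degrees of freedom. Anyone given an SD and its n can attach the interval, so leaving it out of the plan loses no information.

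**What the plan already yields.** Section 9 provides means and standard errors, and SD = SE × √n for whichever quantity the standard error describes. It also provides comparisons between exercises, whose error term would reflect within-person variation if the ANOVA is run as repeated measures. The list of summaries is worded as including these items, so an SD of change is not excluded. Section 12 has each participant's recordings and questionnaire answers stored under a participant code, so measurements can be paired within person. From those, the SD of change for each exercise, the SD of the Acapella–Tube difference and the correlation can all be computed.

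**The case for a change.** The strongest case for a change is that it would be cheap: two sentences and no new data. It would give an objective that the investigators set themselves a defined output. With effect sizes unknown, variability estimates may be among the most useful products of the study, and naming candidate outcomes beforehand would stop the sizing outcome being picked after the results are seen. The standard error gives the needed SD only if it is of the paired change, and Section 9 does not say so.

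The facts in this case stand: the sizing outcome is not named and the standard error is ambiguous. Its force is limited in three ways.

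- A paired SD is the key input only if the later study is also within-person. The protocol speaks only of possible or larger future work. Section 1 looks ahead to compliance and better outcomes of therapy, which could lead to a parallel-group trial. That trial would be sized on the raw SD, perhaps with a baseline correlation.
- It would be too strong to say that nothing is planned for this objective. Means, standard errors and between-exercise ANOVAs are inputs to it; their form is what is unspecified.
- The harm needs two conditions: publication of raw summaries only, and a planning team without access to the data. The investigators themselves would face neither obstacle.

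**Conclusion.** The omission is genuine, but it is missing detail and not an error, and no change to the plan is needed. No stated rule gives a wrong answer, no estimate or test in this study would come out differently, and no data needed for future sizing go uncollected. In a declared feasibility study of 30 people, it is reasonable to leave the sizing outcome and the relevant SD until the next design is known. An analyst would then take the SD of change from the paired data, or the raw SD for a parallel-group trial.

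The size of the issue, if someone had only raw summaries, is a 3.8-fold spread in an illustrative sample size (34 to 9). This rests on an assumed ρ of 0.5 to 0.9, a target of 0.5 raw SD, 80% power, two-sided 5% and a within-person successor study, none of which is in the documents. The imprecision of an SD from 10 patients (0.69 to 1.83 times the estimate, assuming normal data) comes from the sample size, and wording in Section 9 would not reduce it. The conclusion assumes that the coded individual data remain available to those who plan the next study. When the results are written up, it would be good practice to say which quantity each standard error describes.

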10. PATIENT AND PUBLIC INVOLVEMENT (PPI)

Patients are the participants (research subjects) in this study, and as such, are a key part of the research process. Not only will they participate in the two interventions being investigated, but their opinions of the recruitment process and experience of data collection will be sought so as to inform a future and larger study. It is hoped that in this way we will be able to ensure the smoothest and optimal patient experience for future studies.

However, in terms of the present proposed study, as it is a rather small scale feasibility study we do not anticipate there will be any need for patient or public involvement in the research management, research undertaking, analysis or finding dissemination. However, we did seek

the input of members of the public (voice clinic attendees) to help us hone the clarity of our patient information sheets and settle on the amount of participant compensation (gift certificates and travel costs). As a result of their input, the information sheets were revised and compensation levels increased.

11. FUNDING AND SUPPLY OF EQUIPMENT

The study funding has been reviewed by the UCL/UCLH Research Office, and deemed sufficient to cover the requirements of the study. NHS costs will be supported via UCLH and/or the Local Clinical Research Network.

The research costs for the study have been supported by a grant from Smith's Medical in the amount of £14,257 (inclusive of one year of 0.2 WTE backfill of clinician time, equipment upgrade, consumables, participant incentive voucher purchase, travel and accommodation at international conference). Smith's Medical will also be supplying twenty-six (26) Acapella Choice Devices to be used by the participants of this study (to supplement the four devices which the department already holds in stock).

All instrumental assessment to be carried out using equipment already present in the Royal National Throat, Nose and Ear Hospital's Voice Lab, namely a PENTAX Computerised Speech Lab (Model 4150), EGG Module (Model 6103) and Phonatory Aerodynamic System (Model 6600).

12. DATA HANDLING AND MANAGEMENT

The study is compliant with the requirements of General Data Protection Regulation (2016/679) and the Data Protection Act (2018). All investigators and study site staff will comply with the requirements of the General Data Protection Regulation (2016/679) with regards to the collection, storage, processing and disclosure of personal information, and will uphold the Act's core principles. UCLH is the data controller; the UCLH Data Protection Officer can be contacted on [contact] The data processors are UCLH. The study will be collecting the following personal data:

- Basic demographic and diagnosis data drawn from medical and electronic records, (i.e. age, gender, findings of ENT exam)

Experimental data, which is non-identifiable, that will be collected in the course of the research include:

- Electronic voice recordings, electronic intraoral pressure recordings, electroglottographic recordings and patient questionnaire data.

Electronic files will be anonymised with participant codes and held on the hospital shared drive, questionnaires will be codified into an electronic spreadsheet and the hard copies stored in the study file, which is maintained in the RNTNESLT (ENT) Department. The study file will contain a record of all written consents and a list of participant codes; the study file will not leave the premises.

Instrumental data, anonymised by participant code, will occasionally be electronically transferred to the study's co-author, [name] [name] (Visiting Researcher, Academy of Performing Arts in Prague, Malá Strana, Czechia), for specialist analysis. This will not include personally identifiable data.

13. PEER AND REGULATORY REVIEW

The study has been peer reviewed in accordance with the requirements outlined by UCLH.

This study has been peer reviewed within UCLH and by an independent and relevant peer reviewer on 13th November 2018 and 21st November 2018, respectively. The Sponsor has accepted these reviews as adequate evidence of peer review.

14. ASSESSMENT AND MANAGEMENT OF RISK

The manufacturer cautions against using excessive pulmonary pressures with the Acapella Choice (i.e. in excess of 20 cmH₂O) as this might lead to an adverse effect in those who are sensitive to increased transpulmonary pressures. The manufacturer advises that adverse effects might include:

- Increased work of breathing that might lead to hyperventilation
- Increased cranial pressure
- Cardiovascular compromise (myocardial ischaemia, decreased venous return)
- Air swallowing with increased likelihood of vomiting and aspiration
- Claustrophobia
- Pulmonary barotraumas

In our recent pilot study involving only normal and healthy volunteers, not one of the 22 participants exceeded this level of 'excessive' pressure. During the pilot, the mean pressure during Acapella exercise was in fact only 6.22 cmH₂O, (range 3.98-16.75 cmH₂O). As the participants in this study are more likely to have lower pulmonary pressures (owing to an expected higher mean age), it seems unlikely that this pressure will be exceeded. Additionally, the list of adverse effects is indeed related to the list of contraindications for PEP exercising (i.e. those who are sensitive to increased transpulmonary pressure), and these are included in our exclusion criteria. Furthermore, the experimental protocol involves live monitoring intraoral pressure during exercising. As such, the task will be aborted if this upper pressure limit is being reached.

The other task examined in this study ("Tube") is part of the normal input of our department, is limited by design to 5 cmH₂O intraoral pressure and has never resulted in the need to report an adverse effect in the many years of its therapeutic use at the Royal National Throat, Nose and Ear Hospital.

15. RECORDING AND REPORTING OF EVENTS AND INCIDENTS

15.1. Definitions of Adverse Events

Term	Definition
------	------------

Adverse Event (AE)	Any untoward medical occurrence in a patient or study participant, which does not necessarily have a causal relationship with the procedure involved.
Serious Adverse Event (SAE).	Any adverse event that: 
 ● results in death, ● is life-threatening*, ● requires hospitalisation or prolongation of existing hospitalisation**, ● results in persistent or significant disability or incapacity, or ● consists of a congenital anomaly or birth defect

*A life- threatening event, this refers to an event in which the participant was at risk of death at the time of the event; it does not refer to an event which hypothetically might have caused death if it were more severe.
 
** Hospitalisation is defined as an in-patient admission, regardless of length of stay. Hospitalisation for pre-existing conditions, including elective procedures do not constitute an SAE.
	

15.2. Assessments of Adverse Events

Each adverse event will be assessed for severity, causality, seriousness and expectedness as described below.

15.2.1. Severity

Category	Definition
Mild	The adverse event does not interfere with the participant’s daily routine, and does not require further procedure; it causes slight discomfort
Moderate	The adverse event interferes with some aspects of the participant’s routine, or requires further procedure, but is not damaging to health; it causes moderate discomfort
Severe	The adverse event results in alteration, discomfort or disability which is clearly damaging to health

15.2.2. Causality

The assessment of relationship of adverse events to the procedure is a clinical decision based on all available information at the time of the completion of the case report form.

The following categories will be used to define the causality of the adverse event:

Category	Definition
Definitely:	There is clear evidence to suggest a causal relationship, and other possible contributing factors can be ruled out.
Probably:	There is evidence to suggest a causal relationship, and the influence of other factors is unlikely
Possibly	There is some evidence to suggest a causal relationship (e.g. the event occurred within a reasonable time after administration of the study procedure). However, the influence of other factors may have contributed to the event (e.g. the participant’s clinical condition, other concomitant events).
Unlikely	There is little evidence to suggest there is a causal relationship (e.g. the event did not occur within a reasonable time after administration of the study procedure). There is another reasonable explanation for the event (e.g. the participant’s clinical condition).
Not related	There is no evidence of any causal relationship.
Not Assessable	Unable to assess on information available.

15.2.3.Expectedness

Category	Definition
Expected	An adverse event which is consistent with the information about the procedure listed in the manual of operation or clearly defined in this protocol.
Unexpected	An adverse event which is not consistent with the information about the procedure listed in the manual of operation* or clearly defined in this protocol.

* this includes listed events that are more frequently reported or more severe than previously reported

